## **SWEDISH ABSTRACT**

Patienter med samtidig hjärt- och kärlsjukdom, njursvikt och diabetes representerar nästan hälften av alla patienter som vårdas vid hjärt-, njur- och diabeteskliniker, och cirka 15% lider av alla tre. Andelen patienter med flera samtidiga kroniska tillstånd ökar markant med åldern. Dessa komplicerade sjukdomar interagerar, och behandling av en påverkar de andra. Trots detta har en ökande subspecialisering medfört att kardiologen "bara" behandlar hjärtat, nefrologen "bara" njurarna och endokrinologen "bara" diabetes. Studier och riktlinjer följer samma mönster. I bästa fall leder detta till att patienterna får besöka flera specialister inom varje fält. I värsta fall till onödigt upprepade undersökningar, underdiagnostik och underbehandling. Ur patientperspektivet finns ett stort behov av samordning och förbättring av vården, inte bara för att minska sjukdomsprogression utan även för att optimera livskvalitet.

Vi avser att studera om behandling och utfall för patienter med samtidig hjärtkärlsjukdom, njursvikt och diabetes kan förbättras genom en ny vårdmodell. Vi har utformat en integrerad klinik som hanterar alla tre förhållandena vid samma besök, med ett personcentrerat teambaserat tillvägagångssätt mellan patienter, sjuksköterskor och läkare, med två terapikonferenser per vecka med dedikerade och utbildade kardiologer, nefrologer och endokrinologer. Vid dessa utvecklas optimerade vårdplaner, och vid återbesök och telefonkontakter implementeras dessa tillsammans med patienten.

Interventionen studeras i en randomiserad kontrollerad studie (CareHND; n = 131) vid HND-centrum, en unik integrerad öppenvårdsklinik i Stockholm och i en matchad långtidskohortuppföljning vid "The Integrated Care Clinic", i Vancouver, den första integrerade hjärt-njur-diabetes- kliniken i världen. 62 patienter har randomiseras i pilotstudien.

Vår huvudhypotes är att HND-centra resulterar i bättre vård, från flera aspekter, med ett ur ett helhetsperspektiv lägre resursutnyttjande.

## ENGLISH ABSTRACT

Patients with concomitant cardiovascular disease, renal dysfunction and diabetes represent almost half of all patients attending cardiac, kidney and diabetes clinics, and about 15 % suffer all three. This proportion of patients with multiple chronic conditions increase markedly by age. These complicated diseases interact, and treatment of one affect the others. Despite this have a progressive subspecialisation caused cardiologist to treat “only” the heart, nephrologists “only” the kidneys and endocrinologists’ “only” diabetes. Studies and guidelines follow the same pattern. At best this require patients to visit specialists in each field; at worst result in redundant examinations, under-diagnosis and under-treatment of comorbidities. From the patient perspective, there is a great need for coordination and improvement of the care, not only to reduce disease progression but also to optimise quality of life.

[figure not shown]
We aim to study if the treatment and outcome for patients with concomitant cardiovascular disease, renal dysfunction and diabetes can be improved through a new model to deliver healthcare. We have designed an integrated clinic to handle all three conditions at the same visit, with a person-centered team-based approach between patients, nurses and physicians, with bi-weekly therapy conferences by dedicated and educated cardiologists, nephrologists and endocrinologists. At these, optimised care-plans are developed, and at following team-visits and phone contacts, these are implemented.

The intervention will be studied in a randomised controlled trial (CareHND; n=260) at HND-centrum, a novel integrated outpatient clinic in Stockholm, and a matched long-term cohort follow-up at the Integrated Clinic in Vancouver, the first integrated heart-kidney-diabetes clinic in the world. 62 patients have been randomized in the pilot study.

Our main hypothesis is that HND-centra results in better care, from several aspects, at lower overall burden on the health care system.

## Background – co morbidities more common than not

Cardiovascular diseases (CVD) are the leading cause of death both in Sweden and globally, and if not prevented and treated optimally causing increased morbidity, impaired quality of life and premature death [2]. Hyperlipidemia, smoking, hypertension and diabetes are well established as the most powerful modifiable risk factors for CVD. CKD and diabetes share many of the mechanisms causing accelerated vascular aging [3], and in recent years chronic kidney disease (CKD) has emerged as a factor of equal importance [4]. About 20% of the population in developed countries have hypertension, while the prevalence exceeds 50% in those above age 60 years [2]. The prevalence of chronic kidney disease (CKD), defined by reduced glomerular filtration rate (GFR) or albuminuria, is in the range of 10–13% in the general population and about 30% in those above 65 years of age [5]. The prevalence of diagnosed diabetes mellitus in adults  $\geq 65$  years is 10-20% in Sweden, compared to 27% in North America, and an additional 50% have pre-diabetes [6]. In addition, data from NHANES 2005–2006 show that 46% of diabetes cases may remain undiagnosed [7]. Thus, with this high prevalence numbers, the risk of having several of these diseases is high. In fact, in patients 65 years or older, it is more common to have two or more chronic conditions, than just one [8]. Patients with multiple chronic conditions receive a remarkable amount of health-care recourses (Fig. 1.). However, in the Swedish health-care system, no one is coordinating these interventions. Least of all, the patient, whom often feel out of control, their daily lives filled with taking pills, injections, checking blood-glucose levels, seeing doctors and nurses, and doing blood works [1].

**Fig 1.** Overview of healthcare consumption during 18 months for a 75 years old man with concomitant cardiovascular disease, CKD and diabetes; a typical “HND-patient”. Adapted from “Team for the elderly, vision and reality” [1]. Review shows medical notes on the medical centre taken by 6 different doctors, 20 nurse practitioners, two RN, and regular notes from many more during 149 days of hospitalisation. OC: occupational therapist.

## Background – co morbidities and compound risk

The reasons why kidney failure causes heart disease, and vice versa (the cardiorenal syndrome) is still incompletely understood [9]. Patients with concomitant cardiovascular disease, renal dysfunction and diabetes are despite their high risk and high health care consumption often inadequately treated, since an increasingly specialised medical care too often focus on only one part of the disease panorama. Current studies and guidelines follow the same pattern.

In acute coronary syndromes, the single most common cause of death worldwide [2], approximately 40% of the patients have at least moderate kidney dysfunction with an eGFR below  $60 \text{ mL/min/m}^2$  [10]. The 1-year-mortality among these is about 25%, compared to 5% in patients with normal renal function [10]. The increased mortality in CKD patients after an acute coronary event is directly related to decreasing kidney function [4]. This may in part be due to the fact that patients with kidney dysfunction are receiving less active treatment, such

as early revascularisation [11], but may also be caused by a range of disturbances in for instance haemostasis and vascular function [3]. The lack of guidelines, which can be attributed to limited clinical data, as the majority of randomised trials in acute coronary syndromes so far have often excluded CKD patients [12].

More than 80% of all cardiovascular deaths can be delayed using changes in life-style and commonly prescribed drugs [13]. Despite this, many patients never receive the full benefits from these interventions because of frequent under-diagnosis, late presentation and consequent under-treatment [14,15]. This is particularly an issue for subjects with complex diseases such as concomitant cardiovascular disease, kidney dysfunction and diabetes.

### **Background – Multidisciplinary secondary preventive interventions**

There exists good evidence for a range of measures that reduce the risk of relapse in patients with established cardiovascular disease [16]. The consensus is that all these interventions should take place simultaneously [16]. An excellent example of how efficient this approach can be when implemented rigorously is the STENO-2 study, where a multifactorial intervention in type 2 diabetes halved the absolute risk of death over 13 years [17]. However the STENO-2 study excluded patients with concomitant heart disease or kidney failure, notwithstanding their higher risk. Despite the high indication for optimal treatment, we have shown that only one in four patients with hypertension reach target blood pressure [14], and that few patients reach a good secondary prevention after myocardial infarction [15]. Traditional health-care models ascribe this to lack of patient compliance; a term implying that the patient and not the physician is at fault.

### **Background – Person-centered care in chronic disease management**

Chronic diseases require a different way of providing care than acute, since almost all the actual care is done by the patient him/herself through changes in lifestyle and actively taking medications. This requires a well-informed and involved patient; informed at a level which the patient can take in. A model that in recent years been shown to produce very positive results also in chronic cardiovascular diseases is person centered care [18-20]. Person-centered care can be described as a partnership between patients and professional caregivers, where the patient is seen as a person with resources and abilities to participate in their own care [18]. The prerequisite for being able to provide person-centered care is that health professionals thoroughly understand not only the patient's illness but also the patient's situation in life. After establishing this relationship, a plan with goals and strategies for implementation and short - and long-term follow-up can be made. Realistic short-term successive goals on life-style improvements are usually an important part.

### **Background – Integrated care units**

HND-centrum is a new way of conducting health care in the form of an integrated care unit [21]. Pilot studies using this approach have shown promising results, for instance the North West London Integrated Care Pilot for elderly patients with diabetes [22]. It is yet not clear how to efficiently design and develop integrated care units [21]. HND-centrum enables studies on how to design these to maximise patient value, in terms of health outcomes, and efficiency. The research aims to increase our knowledge on how health processes are formed within the HND-centrum; how staff integrates their knowledge and develops health care, and how the value of this can be measured by the ratio of outcomes and cost.

### **Purpose and aims**

Patients with concomitant cardiovascular disease, renal dysfunction and diabetes represent a large proportion of all patients in cardiology, nephrology and diabetology. The progressively increased subspecialisation has caused the cardiologist to treat "only" the heart, nephrologists "only" the kidneys and endocrinologists' "only" diabetes. Current studies and guidelines

follow the same pattern. At best, this requires the patient to visit multiple specialists in each field; while at worst, may result in serious under-diagnosis and under-treatment of co-morbidities. From the patient's perspective, there is a great need for coordination and improvement of the care, not only to reduce the rate of disease progression but also to optimise quality of life.

We will use HND-centrum, a new integrated outpatient clinic, which opened in Nov. 2013 as Sweden's first, and the second in the world after Vancouver, Canada. HND-centrum is staffed by experienced specialists from the three specialties, by nurses and paramedics. Already from the start the HND-centrum implements a person-centred healthcare. The clinical part of the project is supported by Danderyd Hospital.

Our main hypothesis is that HND-centrum results in better care, from many aspects, at a lower overall cost to society. This is an application for a grant to show this through a randomised trial (**Care-HND**).

[figure not shown]
## Project plan

HND-centrum is an outpatient clinic that will replace visits to several doctors and nurses, where instead competence and care are organised and integrated around the patient.

The recently initiated study **Care-HND** (Fig. 2) will randomise 260 patients to HND-centrum or standard care.

The sample size is based on a power calculation for the combined outcome: death, readmission for heart failure, myocardial infarction, PCI/CABG, end stage renal failure or TIA / stroke with two years follow up.

The same power for quality of care and health care consumption require fewer patients, 131, to be randomized, and followed for 1 year.

**Figure 2.** Flowchart for the **Care-HND** study where 260 patients are randomised to HND-centrum or standard care. After one year's time crossover to the intervention arm is permitted. Intention-to-treat analysis.

### Inclusion criteria – **Care-HND**:

- 1 - *Established cardiovascular disease* (history of myocardial infarction, angina, or heart failure requiring hospitalization. Previous stroke or TIA with certain diagnosis), as well as:
- 2 - *Diabetes mellitus type 1 or 2* (treated diabetes, or new onset diabetes according to WHO criteria or  $\text{HbA1C} > 48$ , and symptoms, as well as:
- 3 - *Established kidney disease* ( $\text{eGFR} < 60 \text{ mL/min/m}^2$  calculated with the CKD-EPI formula, or an average of the CKD -EPI and Cystatin-C eGFR, or borderline GFR but concomitant microalbuminuria, or macroalbuminuria, or kidney transplant).

### **Integration with quality registries**

The majority of HND patients will continuously be registered in the national quality registries SWEDEHEART, National Diabetes Register and the Swedish Renal Registry. These in combination with National Welfare records on morbidity and mortality, and the Prescription Registry will be used for analysis of outcomes. Registry data will be used to characterize patients that meet the criteria HND but that are not randomised, in order to understand potential selection bias.

### **Value-based health care**

Value-based health care analyse outcome measures in relation to expenses over the whole course of the disease [23]. The outcome measures are described at three levels: immediate effects, time to recovery, and long-term consequences. Data from hospital management, process mapping and quality registry data will be used to monitor the randomised trial. From cost per patient (CPP), the estimated value for patients and society will be determined.

### **Interprofessional teams, clinical microsystems and inter-professional learning**

HND causes changed work routines for all involved professions, specialties including patients. This can be seen as a clinical microsystem around the patient. Today there are no studies that illustrate how members of such microsystem work together in this type of clinic. We aim to describe and understand this using observations, interviews, and surveys of the personnel.

### **Sample Collection for bio banking and biochemical analyses**

Patients will be tested regularly for clinical routine tests such as electrolytes, CRP, urinary albumin/creatinine ratio, cystatin-C, and PTH. Patients will also give blood / plasma / serum / urine for a biobank for later analysis within:

*Transcriptomics*: genetics and RNA including mRNA, SNPs and CNVs.

*Proteomics*: fibrosis markers PICP, C1TP, TIMP1. Inflammatory markers as IL6, IL8, MCP1, CXCL16.

*Renal function markers*: as NGAL KIM1, NHE3, IL18.

*Hemodynamic markers*: MR- proADM, copeptin, titin.

*Markers of haemostasis*: PAI-1 AG, D- dimer, VWF, E- selectin, and OHI. Free RNA and DNA. Microparticles.

*Metabolomics*: insulin, leptin, GLP-1, PYY, GIP.

A number of patients will give leukocytes.

### **(Re-)defining health related outcome**

From a patients' perspective many more things matter than mortality, and we will develop a combined outcome-model based on the collaborative effort between Karolinska Institutet, Harvard Business School, and Boston Consulting; ICHOM ([ichom.org](http://ichom.org)).

In 2006, [name] wrote the well-known book, Redefining Health Care leading to the work redefining health related outcome. This concept has clear advantages by not selecting a single outcome measure as the only one to focus on, but takes into account all issues that may impact on the patient's life and quality of life. A model has been developed

for a few common diseases, such as Myocardial Infarction (Fig. 3). However, myocardial infarction is a disease with a clear event in time; while HND are chronic conditions. Thus, the model will need some re-development for HND, in collaboration with LIME and ICHOM.

**Figure 3.** International Consortium for Health Outcomes Measurement (ICHOM) is a non-profit organization founded by Harvard Business School, Karolinska Institutet and Boston Consulting Group with the purpose to improve health care studies worldwide by measuring and reporting patient outcomes in a standardized way.

## Primary outcome measures

### *Disease progression (n=260)*

Combined death or readmission due to heart failure, myocardial infarction, PCI/CABG, end stage renal failure, acute renal failure or TIA / stroke.

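### Should planned PCI/CABG be removed from the primary disease-progression composite because the care is unblinded?

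*Protocol*

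**What the plan says.** Under Primary outcome measures, Disease progression (n=260), the outcome is "Combined death or readmission due to heart failure, myocardial infarction, PCI/CABG", and the list then goes on to renal and cerebrovascular events. The Project plan bases the sample size of 260 on a composite of "death, readmission for heart failure, myocardial infarction, PCI/CABG, end stage renal failure or TIA / stroke with two years follow up". Both lists name PCI/CABG without saying whether the procedure must be urgent or whether elective and staged procedures count. (The lists differ on acute renal failure, which is a separate matter.) Nothing elsewhere in the Protocol narrows the component.

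Three other places bear on the point:

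- The English abstract describes therapy conferences that include cardiologists: "At these, optimised care-plans are developed, and at following team-visits and phone contacts, these are implemented".
- The background section on compound risk discusses higher mortality in kidney patients after an acute coronary event. It says "This may in part be due to the fact that patients with kidney dysfunction are receiving less active treatment, such". The sentence goes on to give revascularisation done early as its example and to allow for other causes.
- Integration with quality registries says "The majority of HND patients will continuously be registered in the national quality registries". It does not mention admission type.

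The statistics section plans a log-rank test and a Cox model on time to outcome, with the primary outcomes analysed by intention to treat.

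**The concern.** One arm attends a different clinic, so patients and clinicians know the allocation. Death or stroke does not arise from an elective treatment decision, but a planned PCI or CABG partly does, and here the decision is taken by people who know the arm. The care model is meant to remedy under-diagnosis and under-treatment. If better case-finding at HND-centrum led to more planned revascularisation, good care would be scored as disease progression. If better prevention led to fewer, the component would add to the apparent benefit.

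In a time-to-first-event analysis a planned procedure can be the first event and so enters the hazard ratio directly. A procedure during a readmission for infarction is neutral, because the infarction already counts. The difficulty therefore lies mainly with planned procedures. At stake is whether the composite hazard ratio can be read as disease progression, and how much power the component adds or removes. The apparent remedy is to count only unplanned procedures.

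**Working it through.** **The plan's own figure.** The sample size of 260 cannot be reproduced. The Protocol gives no event rate, effect size, significance level, power, allocation ratio or dropout for it. What follows is illustration on assumed inputs.

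**Assumed inputs.** 1:1 allocation (130 per arm), two-sided 5%, two-year control risk p = 0.40. PCI/CABG is a share s = 0.10 or 0.20 of control first events, and half of it is planned (q = 0.5). The hazard ratio on the other components is 0.541, the value that gives 80% power at this p and n.

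**Formulas.** Let mu and mp be the hazard ratios for unplanned and planned procedures.

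- All PCI/CABG counted: HR = (1−s)×0.541 + s(1−q)×mu + s×q×mp.
- Unplanned only: HR = [(1−s)×0.541 + s(1−q)×mu]/(1−s×q), with the control hazard multiplied by (1−s×q).
- Events = 130×[p + 1 − (1−p)^HR].
- Power = Φ(√(events/4)×|ln HR| − 1.96).

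**Baseline.** With HR = 0.541, events = 130×(1.40 − 0.60^0.541) = 83.4. Power = Φ(4.57×0.614 − 1.96) = 80%.

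**One worked case.** Take s = 0.20, mu = 1 and mp = 1.5.

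- All counted: HR = 0.4328 + 0.10 + 0.15 = 0.683, 90 events, power 44%.
- Unplanned only: HR = 0.5328/0.90 = 0.592, control risk 1 − 0.60^0.9 = 0.369, 79 events, power 64%.

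**Unplanned procedures unaffected (mu = 1).** Each pair is s = 0.10 / s = 0.20.

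| Planned ratio | All counted | Unplanned only | Gain from restricting (points) |
|---|---|---|---|
| 0.54 | 75% / 69% | 73% / 64% | −2 / −5 |
| 0.70 | 73% / 65% | 73% / 64% | 0 / −1 |
| 1.0 | 69% / 57% | 73% / 64% | +4 / +7 |
| 1.5 | 63% / 44% | 73% / 64% | +10 / +20 |

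Break-even planned ratio: 0.71 / 0.74.

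**Unplanned procedures fall like the rest (mu = 0.541).** Unplanned-only power is 78% / 77%. Counting all gives 80% / 80%, 78% / 77%, 75% / 69% and 69% / 56% at the same four planned ratios. Break-even is about 0.70.

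**A milder case.** With s = 0.10, 30% of procedures planned, mp = 1.0 and mu = 0.541, counting all gives HR 0.555 and 77% power. Unplanned-only gives HR 0.541 and 79%, a gain of about 2 points.

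**Cross-check with two proportions.** At a 40% control risk, a risk ratio of 0.596 on every component gives 80% power. With a 20% PCI/CABG share and no effect on it, the intervention risk is 0.40×0.80×0.596 + 0.40×0.20×1.0 = 0.271, and power is about 60%. At a PCI/CABG risk ratio of 1.5 it is about 32%. The pattern is the same.

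These calculations leave out the crossover allowed after one year, which falls within the two-year follow-up and affects every component.

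**What the text supports.** The result turns on mp, and the Protocol gives no information on it. The only revascularisation-specific statement is hedged and concerns early procedures in acute coronary syndromes. Such procedures are unplanned and would stay in a restricted composite. For planned procedures there is only the general language on under-diagnosis and under-treatment.

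**The case for a change.** The strongest case for a change is that this is not a detail left open. The Protocol itself lists the components of a primary outcome, and an elective procedure falls within the wording. The intervention consists of changing how treatment is decided, so a component that depends on treatment decisions is exposed in a way that death, infarction or stroke is not. On the assumed figures the trade-off is also lopsided, with a few points at risk against as many as 20 gained, and the edit would be short.

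Part of this stands. The wording is unqualified, unblinded care is a fair inference from the design, and the composite alone cannot show what planned procedures contributed.

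The step to a new primary definition does not stand. The 20-point gain needs a 20% share, half of it planned, and a 50% rise in planned procedures, none of which is documented. The cost is also more than an edit:

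- The stated sample size was built on a composite that includes PCI/CABG, so it would have to be justified again.
- The English abstract reports 62 patients already randomised in the pilot, and redefining a primary outcome after that in an open trial needs its own defence.
- The Protocol does not promise data on admission type.
- Whether an admission is scheduled is itself partly decided by clinicians who know the arm, so restriction reduces the discretion without removing it.

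**Conclusion.** No change to the plan follows. PCI/CABG is listed without a qualifier, and in this trial a planned procedure partly reflects a treatment decision, so the component may dilute or strengthen the composite hazard ratio. Neither the direction nor the size can be derived from the Protocol. On the assumed inputs, restricting to unplanned procedures moves power by between about −5 and +20 percentage points, with break-even at a planned hazard ratio of roughly 0.70 to 0.74. That describes a choice between two defensible definitions and shows no error in the one chosen.

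What remains is detail that a statistical analysis plan or endpoint charter commonly settles: whether planned procedures count, PCI/CABG reported by arm, and a sensitivity analysis of the composite without planned procedures, or without any PCI/CABG if admission type is unavailable. These steps would show what the component contributed and leave the primary result as defined. No such plan is at hand, so their absence from the Protocol is not a fault. The conclusion would need another look if the documents gave reason to expect the integrated clinic to change the rate of planned revascularisation materially. They give none.
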